9. STATISTICS AND ANALYSIS

9.1. Description of Statistical Methods

Behavioural data measuring the primary outcome (speech function) will be acquired before, during and after brain stimulation using audio and video recordings. Measures of speech fluency (e.g. Stuttering Severity Instrument score, % disfluency) will be taken from these recordings and will be subjected to standard statistical analyses using software such as SPSS. Mixed between- and within-subject designs will be used to compare changes in performance (baseline subtracted) on speech measures between the two groups of participants (tDCS vs. sham). The investigator team have prior experience in statistical analysis of similar behavioural data.

Brain imaging data (MRI) will be analysed using the FMRIB Software Library (FSL) which involve standard approaches for the analysis of functional imaging data. We will also be using novel approaches that allow us to explore functional connectivity, such as probabilistic Independent Component Analysis. The investigator team has substantial with MRI analysis using FSL and SPM.

Vocal Tract Images will be analysed using custom tools implemented in MATLAB.

TMS data will be analysed using custom tools and software to compare measures of cortical excitability within participants between hemispheres, and across time points, and between groups at the baseline timepoint.

While the study is ongoing, we will be able to compare brain and vocal tract imaging, and TMS data in PWS vs controls once we have data from the baseline timepoint. Unblinding is not required for these baseline analyses.

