9.2. The Number of Participants

We plan to recruit 40 PWS and up to 30 controls. The sample size was determined based on previous cross-sectional studies in stuttering, including our own. A sample size of 20 participants in each group is higher than most previous behavioural and functional imaging studies in PWS. This should ensure sufficient sensitivity to detect differences in behaviour, brain structure and function. It should also allow us to determine the relationship between the experimental variables and other measures such as stuttering severity and duration of stuttering. A sample size of 20 for each group should detect a group difference with an effect size of 0.9 at 80% power and 5% false positive rate. For the tDCS study across 5 days, we will compare two groups of 20 PWS. In our previous study, with sample sizes of 15 in each group, effect sizes of 0.93 and 0.50 were obtained for the reduction in the SSI at 1 week and 6 weeks post intervention.

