Study Title: Investigating Non-invasive brain Stimulation To Enhance fluency in People who stutter

Short title: INSTEP Trial
University of Oxford, Medical Sciences Division
IDREC Ethics Ref: R52173/RE001

Document title: INSTEP trial statistical analysis plan
Date and Version No: 23rd October 2017, version 1.0

Chief Investigator: [name], Department of Experimental Psychology, University of Oxford

Investigators: [name], Department of Experimental Psychology, University of Oxford

[name], Department of Experimental Psychology, University of Oxford

[name], Department of Experimental Psychology, University of Oxford

All the investigators declare that there are no conflicts of interest associated with the proposed study.

INSTEP trial statistical analysis plan

We plan to carry out analyses on the 'intention to treat' sample, i.e. including all participants who complete the study. If any participant has data that are group outliers, we will also complete sensitivity analyses (Thabane et al., 2013) by re-running all analyses excluding the relevant participant(s), to evaluate the robustness of the treatment effect. Speech data in people who stutter tends to significantly deviate from a normal distribution. Transformation of these data is problematic for reporting confidence intervals in interpretable units, therefore we will use change scores (baseline subtracted) in the analyses to overcome this limitation. For consistency, we will use this approach of baseline subtraction and analysis of change scores in analysis of other variables even if they do not suffer from the same skewness as the speech data. Variables that are not normally distributed will be analysed using nonparametric methods.

Primary outcome measure

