The primary outcome measure for the trial is the change in stuttering severity, measured using the Stuttering Severity Instrument, version 4 (SSI-4, Riley, 2009). Change from baseline score will be calculated (by subtraction of the baseline) at one week, 6 weeks and 12 weeks following the intervention. Change scores will be entered into a mixed model analysis of variance (ANOVA), with stimulation group (tDCS, sham) as the between subjects factor and speaking task and time point (1 week, 6 weeks, 12 weeks) as the within subjects factor. If a significant interaction between stimulation group and time point is found, separate repeated measures ANOVAs will be performed for each stimulation group or with three planned comparisons between groups at each time point.

Secondary outcome measures

We have three secondary outcome measures:

- i. Change from baseline score in percentage of disfluent syllables, during reading.
- ii. Change from baseline score in percentage of disfluent syllables, during conversation.
- iii. Change in total score on Overall Assessment of a Speaker's Experience of Stuttering (OASES).

Change in percentage of disfluent syllables will be calculated by subtraction of the baseline percentage for reading and conversation separately at one week, 6 weeks and 12 weeks following the intervention. Data will be analysed as described above for the primary outcome measure. Anticipating a significant effect of group in both measures, we will also compare the changes in reading with those in conversation at each time point separately for the tDCS group.

To test for the effects on the OASES measure, we will use a mixed model ANOVA with stimulation group (tDCS, sham) as the between subjects factor and time point (6 weeks, 12 weeks). We will not collect data at the 1-week post-intervention time-point to avoid violating test-retest validity of the scale. If a significant

interaction between stimulation group and time point is found, separate planned comparisons between groups will be performed for each time point.

Other pre-specified measures

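### The primary test is not fixed in advance: non-normal variables move to unnamed nonparametric methods, and change scores do not ensure normality

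*SAP*

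**What the plan says.** The SAP's opening section states the problem: "Speech data in people who stutter tends to significantly deviate from a normal distribution". It rejects transformation because intervals would lose their interpretable units, and continues: "therefore we will use change scores (baseline subtracted) in the analyses to overcome this limitation". The next sentence extends baseline subtraction to other variables "even if they do not suffer from the same skewness as the speech data". The section closes with the switching rule: "Variables that are not normally distributed will be analysed using nonparametric methods".

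Under Primary outcome measure, the SAP sets out a parametric analysis of SSI-4 change at three time points: "Change scores will be entered into a mixed model analysis of variance (ANOVA), with stimulation group (tDCS, sham) as the between subjects factor". Follow-up depends on one term of that model: "If a significant interaction between stimulation group and time point is found, separate repeated measures ANOVAs will be performed for each stimulation group", or else three between-group comparisons, one per time point. The secondary % disfluency outcomes and most other measures are analysed in the same way.

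Protocol 9.1 mentions no alternative: "Mixed between- and within-subject designs will be used to compare changes in performance (baseline subtracted) on speech measures between the two groups".

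**The concern.** The plan is silent on several things that decide which primary p-value is reported:

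- which normality check is used, and at what threshold;
- whether it is applied to the variable, to each arm-by-time cell or to model residuals;
- what happens if only some time points fail;
- which nonparametric method then applies;
- what replaces the group-by-time test. Mann-Whitney and Friedman, the usual menu choices, do not test it.

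Two analysts could follow this SAP to the letter and report different primary results. The authors expect non-normal speech data, so the alternative branch could well be used. The change-score sentence makes the branch look less likely than it is.

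**Working it through.** **Inputs.** From Protocol 9.2: 20 per arm, effect size 0.9, 80% power, 5% false positive rate (two-sided assumed). From the SAP: two arms and three time points. The documents give no distributional figures, so every shape and correlation below is an assumption.

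**1. The plan's own figure.** n per arm = 2(1.960 + 0.842)²/0.9² = 15.70/0.81 = 19.4, rounded up to 20. Power at n = 20 is Φ(0.9√10 − 1.960) = Φ(0.886) = 81.2%, or 79.2% with the noncentral t. The stated 80% reproduces, but for a parametric two-group comparison. No power is given for a rank branch or for the interaction.

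**2. Does subtraction give normality?** If follow-up is roughly proportional to baseline, the change is baseline times a factor and inherits its skew.

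| Assumed raw scores | Raw skewness | Change-score skewness |
|---|---|---|
| Log-normal (log SD 0.8, log-scale correlation 0.8), no effect | 3.6 | −0.4, excess kurtosis about 39 |
| Same, log-scale reduction 0.3 | 3.6 | −2.6 |
| Same, log-scale reduction 0.5 | 3.6 | −3.4 |
| Gamma, 30% reduction | 1.4 | −1.0 |
| Gamma, 50% reduction | 1.4 | −1.7 |

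Subtraction alters the shape but does not ensure normality.

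**3. How often would the switch fire?** This depends on a choice the SAP leaves open. Checking six arm-by-time cells at 5% on truly normal data gives 1 − 0.95⁶ = 26.5% under independence (25% simulated with correlated time points). A single check on residuals fires in about 5%. The two readings send the trial down different branches in about 25% of normal-data trials. With the log-normal scores above, the cell check fires in about 98% and the residual check in 77-83%. These are rates of switching, not error rates.

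**4. Type I error.** With a fixed Shapiro-Wilk gate followed by a t-test or Mann-Whitney on mean change, simulated type I error was 4.4-5.9% across runs. Picking the more favourable of the two tests gives 6.4-6.9%.

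**5. How often does the choice change the conclusion?** On mean change over the three time points, the two tests disagreed in 2.2% of normal-data trials with no effect and 3.9% with an effect. With log-normal scores and no effect, they disagreed in 4.1%. With a log-scale reduction of 0.4 they disagreed in about 20%, with power of 51% for the t-test and 68% for Mann-Whitney. Repeat runs at log SD 0.7-0.8 were mostly in the range 15-20%. At a milder log SD of 0.5 disagreement fell to 4-9%, so the size depends on the skew assumed.

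**6. Power of a baseline-adjusted model.** With normal data, equal variances and baseline-to-follow-up correlation r, the change score has variance 2(1 − r) and the adjusted residual 1 − r². An effect of 0.9 on the change scale therefore becomes 0.9√(2/(1 + r)) after adjustment.

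- r = 0.5: 0.9 × 1.155 = 1.039, power 89%.
- r = 0.9: 0.9 × 1.026 = 0.923, power 81%.

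The comparators are 78-80% for the t-test on change and 76-78% for Mann-Whitney on change. Ranking costs about 2 points; the rest of the gap is baseline adjustment. In the log-normal runs the adjusted model was also ahead of both.

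**The case against.** The strongest defence is that this is a specification gap with little consequence for error control. That stands in part: step 4 shows no material inflation under any single fixed gate. Four stronger readings are tempting, and the documents do not support them.

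- **The false positive rate rises to 9-12.5%.** That needs a fallback of three ungated rank tests, one per time point. The SAP does not say this. A rank test on mean change would mirror the ungated group main effect.
- **Rank methods cannot give interval estimates in SSI-4 points or test an interaction.** They can. Hodges-Lehmann intervals are in SSI-4 points, Mann-Whitney on the difference between two time points tests an arm-by-time contrast, and rank-based factorial methods exist. Protocol 9.1 offers SPSS only as an example of software. The fault is that nothing is named.
- **SSI-4 change will be badly skewed.** The expectation of non-normality is stated for speech data in general, and the log-normal scenario suits % disfluency, a secondary outcome. SSI-4 sums bounded scaled scores (SAP, final paragraph), and the documents say nothing about the shape of its change.
- **The SAP makes an outright false claim about change scores.** The limitation could be read as the loss of interpretable units, which change scores do avoid. The next sentence, on skewness, favours the reading that subtraction is meant to deal with non-normality, although the closing rule accepts that some variables may remain non-normal. The switching problem stands under either reading.

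**Conclusion.** The point holds as a defect of pre-specification. The primary analysis can change after the data are seen, there is no criterion for the change, and the alternative branch has no stated form of the group-by-time test on which follow-up depends. Type I error stays near 5% if one gate is fixed. What is lost is a determinate primary test, the planned interaction test, and roughly 2 to 10 points of power against a baseline-adjusted model (79.2% against 81-89% for r of 0.9 down to 0.5). The choice of test alters the conclusion in about 2-4% of normal-data trials and about 15-20% of trials under strong assumed log-normal skew with an effect. The last figure rests wholly on assumed distributions and should not be read as a forecast for SSI-4. The change is worth making before unblinding, but nothing here shows that the planned ANOVA itself would be invalid.

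**What to change.** Replace the switching rule with one primary model used whatever the normality result: a mixed model of SSI-4 at 1, 6 and 12 weeks with group, time, group-by-time and baseline SSI-4 as covariate. Report the adjusted difference and 95% CI in SSI-4 points, with a bootstrap CI if residuals are clearly non-normal. Adding the covariate alone is not enough, because the switching rule would remain.

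Make a named rank-based analysis, with a Hodges-Lehmann interval, a sensitivity analysis only. Delete the statement that change scores overcome the limitation.

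A permutation p-value is optional. It would have to respect the minimisation on screening SSI-4 (Protocol 6.3), and the documents do not give the details of that algorithm needed to replay it.

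The cost is SAP wording and slightly more programming; all the data are already to be collected. Whether speaking task stays as a factor is a separate question that this change does not settle.

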6.1. Screening and Eligibility Assessment

When a person who stutters contacts the research team and expresses a desire to participate, they will be sent the PIS outlining the procedures and risks involved in taking part. Screening will take place before volunteers have consented to take part in the study. The screening procedure involves obtaining information in line with tDCS, TMS, and MRI safety guidelines (outlined in the standard operating procedure documents developed within the Medical Sciences Division). Also see exclusion criteria in section 6.3 of this protocol. Screening criteria will be assessed by self-report.

Volunteers will also complete a screening assessment of stuttering severity to ascertain eligibility. In the first instance, one of the named investigators will conduct a screening by videoconference (Skype) to determine severity. Stuttering symptoms are typically increased on the first meeting (when participants are unfamiliar with their conversation partner) and over the telephone/ during videoconferencing. Consequently, if stuttering is determined to be of mild severity at this stage, the volunteer will be informed that they do not meet the inclusionary criteria for the study. If stuttering is of mild-moderate or greater severity, a face-to-face appointment will be scheduled, which will take place on University premises, or at the participant's home or office. The severity of stammering as ascertained on this visit will be used to determine whether participants should be enrolled into the study. If stuttering is of mild-moderate or greater severity, then they will be invited to participate.

Once we have determined eligibility, informed consent will be obtained and a suitable appointment will be scheduled, within three months of the screening. If the participant is deemed ineligible, we will first enquire if they wish to participate in other studies within the lab for which they might be eligible. If they do not, all screening data will be deleted (within a month of notification of ineligibility).

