6.3. Randomisation, blinding and code-breaking

A 'minimisation' sampling procedure will be used, whereby participants' stuttering severity as measured during screening with the SSI-4 will be used to assign successive participants to true stimulation or sham stimulation, minimising group differences in severity. A member of the Departmental of Experimental Psychology who is not involved with the study will be in charge of communicating to the project team what code they should use.

On the basis of this randomisation, half the participants will receive true tDCS stimulation and the other half will be in a control group that will not receive stimulation (sham tDCS). In sham tDCS the current is applied for a sufficiently brief duration to avoid any change in cortical

excitability (up to 30 seconds) but long enough to produce the transitory sensation on the skin associated with real tDCS. Although the stimulation is different, each participant will receive exactly the same speech training throughout the study.

The study will also be double-blinded, meaning that the researchers, study staff, and participants will not know whether the condition involves real or sham tDCS. The stimulator used in the study has a 'study' mode to allow the operator to be blind to the stimulation condition.

The person in charge of the randomisation procedure will have the capacity to unblind the data for analysis once data collection is complete. Data may be unblinded during the data collection only in the context of a serious adverse event potentially related to the type of stimulation or if a patient withdraws from the study and needs to be replaced.

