6.4. Baseline Assessments

Following the screening to determine eligibility, participants will complete the baseline assessments (Visit 1, Days 1-2). This visit will take place at OHBA.

During this visit, we will obtain informed consent. We will obtain behavioural measures of speech fluency, as well as complete clinical assessments (SSI-4, OASES). Following this, participants will complete the brain and vocal tract imaging assessments (MRI and TMS) as described below.

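### Free improvement: the primary SSI-4 analysis uses baseline only by subtraction, though the Visit 1 SSI-4 is already collected and could be a covariate

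*SAP*

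**What the plan says.** The SAP, under Primary outcome measure, specifies: "Change scores will be entered into a mixed model analysis of variance (ANOVA), with stimulation group (tDCS, sham) as the between subjects factor". Speaking task and time point (1, 6 and 12 weeks) are the within-subject factors. The % disfluent syllables outcomes follow the same plan, and OASES uses a similar ANOVA at two time points. Protocol section 9.1 agrees: "Mixed between- and within-subject designs will be used to compare changes in performance (baseline subtracted) on speech measures between the two groups". Neither document names a covariate in a primary, sensitivity or nonparametric analysis.

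The SAP's opening paragraph gives its reason for change scores: "Transformation of these data is problematic for reporting confidence intervals in interpretable units". It sends non-normal variables to nonparametric methods.

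The candidate covariates exist. Protocol section 6.4 and Appendix B place an SSI-4 at Visit 1, and Appendix B also places one at Visit 0. Section 6.3 allocates by minimisation: "stuttering severity as measured during screening with the SSI-4 will be used to assign successive participants to true stimulation or sham stimulation". Section 6.1 (Screening and Eligibility Assessment) describes two severity assessments: first, "one of the named investigators will conduct a screening by videoconference (Skype) to determine severity"; then a face-to-face appointment, of which it says "The severity of stammering as ascertained on this visit will be used to determine whether participants should be enrolled into the study". Section 6.3 does not say which one supplies the allocation score.

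Section 9.2 gives the size: "A sample size of 20 for each group should detect a group difference with an effect size of 0.9 at 80% power", with a 5% false positive rate.

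**The concern.** Subtracting baseline fixes its coefficient at exactly 1. A covariate lets the data estimate it. When the true slope of follow-up on baseline is well away from 1, the change score carries avoidable noise. The further the slope is from 1, the more precision adjustment recovers.

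The trial has little to spare. It is sized to just reach 80% power at an effect of 0.9, while section 9.2 itself reports a previous effect of 0.50 at 6 weeks. Precision that needs no new data and no new participants is worth having.

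The stated reason for change scores does not argue against this. With change kept as the response, the adjusted group difference is still in SSI-4 points.

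**Working it through.** **Inputs from the documents.** 20 per arm, effect size 0.9, 80% power, 5% false positive rate (protocol 9.2).

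**Assumptions.** r is the baseline-to-follow-up correlation of SSI-4, taken from 0.5 to 0.9. k is the follow-up SD divided by the baseline SD, taken as 0.8, 1 and 1.2. The effect size is taken to be in change-score SDs, which the protocol does not say. Data are normal and tests two-sided.

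**Step 1. The plan's own figure.** Noncentrality is 0.9 × √(20/2) = 2.846. With 38 df the exact t test has 79.2% power. The normal approximation gives 81.2% and n = 20 per arm. The stated size reproduces.

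**Step 2. Adjustment for Visit 1 SSI-4 at one visit.** In units of baseline variance, the change score has variance 1 + k² − 2rk. The residual variance after regression on baseline is k²(1 − r²), whether the response is change or follow-up. So

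variance ratio = k²(1 − r²) / (1 + k² − 2rk).

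At k = 1 this is (1 + r)/2. One df is charged (37 left), and the variance is inflated by 1 + 1/36 for chance baseline imbalance. Example, k = 1, r = 0.5: ratio 0.75, noncentrality 2.846/√(0.75 × 1.0278) = 3.242, power 88.4%.

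| k | r = 0.5 | r = 0.7 | r = 0.8 | r = 0.9 |
|---|---|---|---|---|
| 0.8: ratio | 0.571 | 0.628 | 0.640 | 0.608 |
| 0.8: power | 95.1% | 93.2% | 92.7% | 93.9% |
| 1: ratio | 0.750 | 0.850 | 0.900 | 0.950 |
| 1: power | 88.4% | 84.3% | 82.2% | 80.1% |
| 1.2: ratio | 0.871 | 0.966 | 0.997 | 0.977 |
| 1.2: power | 83.4% | 79.4% | 78.2% | 79.0% |

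All compare with 79.2% unadjusted. The gain vanishes at k = 1.2, r = 0.8 because the true slope is rk = 0.96, close to the 1 that subtraction assumes.

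**Step 3. Group effect averaged over three visits.** Simulation used 24 correlation patterns, deterministic minimisation on a screening score, the same effect at each visit, and both baseline and screening score as covariates. The power change was +1 to +13 points at k = 1 and +12 to +18 at k = 0.8. At k = 1.2 it was −1 to +2 for r of 0.7 or more and +4 to +8 for r = 0.5.

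**Step 4. What the minimisation score adds.** In those patterns, adding it to baseline changed power by about −2 to +2 points. This depends on the pattern. A separate single-visit simulation set screening, baseline and follow-up equally correlated at k = 1, and there it added more: from 89.7% to 92.0% at r = 0.5 and from 81.7% to 89.5% at r = 0.9. Added without baseline, it gained nothing in that simulation.

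**Step 5. Group-by-time.** At k = 1, baseline-by-time removes (r₁ − r₃)² / [2(1 − r₁₃)] of the variance of the first-to-last visit contrast. Here r₁ and r₃ are the correlations of baseline with the first and last visits, and r₁₃ is the correlation between those visits. For (r₁, r₃, r₁₃) = (0.7, 0.7, 0.7), (0.8, 0.7, 0.8) and (0.8, 0.6, 0.8) the result is 0, 2.5% and 10%. A baseline main effect alone leaves this test unchanged.

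**Step 6. Type I error.** Under deterministic minimisation the unadjusted test rejected in 1.5% to 5.2% of null trials and the adjusted test in 4.6% to 5.5%. Under a biased coin with equal correlations, all analyses, with and without covariates, lay between about 4.4% and 5.6%.

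**The case against.** The strongest case against is that nothing here is wrong. The test is unbiased, the SAP explains its change scores, and minimisation already balances severity. All of that stands.

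The gain also rests on r and k, which the documents do not give. Entry requires an SSI-4 total above 20 (protocol 5.1), which trims the baseline spread and can push k above 1. Truncating four k = 1 patterns at assumed cut points gave k of 1.06 to 1.23. The gain was about unchanged in two patterns and shrank in the other two (single-visit adjusted power from 82% to 80-81%, and from 88% to 85-86%). So the k = 0.8 row should not be read as the expected case.

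The SAP does not say whether group or group-by-time is the efficacy test. If it is the interaction, little is gained. All the figures assume normal data, which the SAP itself doubts, and none were computed for % disfluent syllables or OASES.

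The two candidate covariates may not be distinct. Section 6.1 does not say the videoconference screen is scored with the SSI-4. Appendix B lists one SSI-4 at Visit 0, with videoconference speech only. Live speech first appears at Visit 1, where eligibility and randomisation are also ticked. The allocation score could therefore overlap with, or be, the Visit 1 score.

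These points limit the size of the claim and shape the remedy. They do not remove it: the covariate is already collected, and the largest single-visit loss in the grid is one point.

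**Conclusion.** This is a free improvement worth making, not a defect in the planned test. At one visit, for an effect of 0.9 change-score SDs, baseline adjustment moves power from 79% to somewhere between 78% and 95%. The result is 80-88% if follow-up and baseline spread are equal, and about nil gain if follow-up is more variable and r is 0.7 or more. The benefit is for the group effect and the per-visit group comparisons.

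Three stronger readings are tempting, and the documents support none of them.

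- A reader might infer that leaving out the minimisation factor biases the estimate or invalidates the type I error. It does neither in these checks. Any conservatism depends on the allocation algorithm, which section 6.3 does not specify, and on the correlations.
- A reader might infer that the screening score matters as much as Visit 1 SSI-4. In the 24 patterns almost all the gain came from Visit 1. The larger contribution under equal correlations needs an assumption the documents do not supply.
- A reader might infer that adjustment makes the trial adequate for smaller effects. At an effect of 0.50, single-visit power is 34% unadjusted and 34-42% adjusted at k = 1. Adjustment does not replace a sample-size justification.

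**What to change.** Amend the SAP before unblinding:

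1. Keep change in SSI-4 as the response and keep the planned factors. Add Visit 1 SSI-4 as a continuous covariate for the group effect and the per-visit group comparisons, with a baseline-by-time term so that its slope can differ by visit.
2. For % disfluent syllables in reading and in conversation, and for OASES, add each outcome's own baseline.
3. Where a variable goes to nonparametric methods, name a baseline-adjusted counterpart, such as a rank-based ANCOVA or a permutation test on baseline-adjusted residuals.
4. Secondary: state which screening assessment in section 6.1 supplies the SSI-4 score used in section 6.3. If it is a different measurement from the Visit 1 SSI-4, include it as a covariate too, chiefly to match the analysis to the allocation.

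The cost is SAP wording and a few degrees of freedom. No extra data, visits or participants are needed.
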